Primary hepatocellular carcinoma (HCC) is a typical hypervascular tumor. Its occurrence, development, metastasis, and invasion are all closely related to angiogenesis. A randomized, open-label, multi-center, Phase II clinical trial evaluating apatinib mesylate in advanced hepatocellular carcinoma was conducted from 2010 to 2013, led by the 81th Hospital of the Chinese People's Liberation Army. A total of 121 subjects received the medication. In the full analysis set, the median time to progression (mTTP) was 4.21 months and median overall survival (mOS) was 9.71 months in the 850 mg group. The mTTP was 3.32 months and mOS was 9.82 months in the 750 mg group. There were no statistically significant differences in mTTP and mOS between the 850 mg and 750 mg groups. The incidence of adverse reactions was 95.71% in the 850 mg group and 90.20% in the 750 mg group. The incidence of severe adverse reactions was 58.57% and 58.82%, respectively. The difference was not statistically significant. Therefore, 750 mg was the recommended dose for Phase III clinical trials due to its superior tolerability. The recommended dosing regimen is 750 mg, p.o., q.d., continuous administration in

cycles of 28 days (not including treatment interruption), until disease progression or unacceptable toxicity. Treatment can be interrupted (no more than 2 weeks) or the dose can be adjusted to 500 or 250 mg in case of Grade 3/4 hematologic or non-hematologic toxicities.

A randomized (2:1), open-label, placebo-controlled, multi-center, Phase III clinical trial evaluating the efficacy and safety of apatinib as second-line treatment of advanced HCC is currently underway. Patients with advanced HCC who failed sorafenib or systemic chemotherapy or patients with relapse or unacceptable toxicity were recruited. As of December 2017, a total of 400 subjects were enrolled. Adverse events that have been observed include proteinuria, elevated blood pressure, thrombocytopenia, hand-and-foot syndrome, and elevated total bilirubin. For details regarding apatinib mesylate, please refer to the prescribing information for apatinib mesylate and the Investigator's Brochure provided by the sponsor.

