5.3. Dose Modifications

The dose of the investigational drugs may be modified according to the toxic side effects of the investigational drugs. The options of dose modification include: dose interruption, dose reduction, change in route of administration, and discontinuation.

In this study, SHR-1210 treatment may be interrupted for up to 12 weeks;

In addition to treatment interruption, the dosage of SHR-1210 can be reduced to 3 mg/kg, q2w, for subjects with a body weight of less than 50 kg during the treatment.

Dose modifications caused by apatinib-related toxicity include: dose interruption, modification of method of administration (first modification: 5 days of drug administration followed by 2 days of dose interruption; re-modification: 7 day of drug administration followed by 7 day of dose interruption), and dose termination. A changed route of administration for apatinib shall never be resumed for the subject.

If apatinib-related AE occurs during the study, such as hypertension, proteinuria, or hand-and-foot syndrome, apatinib may be interrupted, and can be resumed, administered in a modified route, or discontinued accordingly when the toxicity resolves. Subjects may continue SHR-1210 as monotherapy if apatinib treatment is discontinued.

For immune-related toxicity occurring during the trial, such as immune-related pneumonia, hepatitis and colitis, the dosing of SHR-1210 and apatinib should be interrupted as appropriate. The dosing can be resumed when the toxicity returns to Grade ≤ 1 or baseline levels (for subjects with abnormal laboratory measurements such as ALT/AST and TBIL at baseline). The dosing of SHR-1210 should be resumed first. The dosing of apatinib can be resumed when no significant abnormality is observed within 7 to 14 days after SHR-1210 administration. The route of subsequent administration of apatinib should be modified.

During the study, in case of \geq Grade 3 immune-related pneumonia, \geq Grade 3 elevation in TBIL (recurrent), Grade 4 elevation in ALT/AST (recurrent), other Grade 4 immune-related toxicities (except for hypothyroidism), Grade 4 injection reactions, or the interruption of SHR-1210 administration for more than 12 weeks due to immune-related toxicity but the toxicity can still not return to \leq Grade 1 or baseline levels (subjects with baseline abnormality), the administration of SHR-1210 should be terminated permanently.

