### 5.5.2. Adverse events

All AEs are encoded by using MedDRA v24.0 and graded using NCI-CTCAE v4.03. For the same SOC and/or PT, multiple cases of the same events occurred in one subject will be counted only once. For the same AE reported in one subject multiple times but varying in CTCAE grade, the AE of the greatest grade will be enumerated.

Treatment-emergent adverse events (TEAEs) are defined as any adverse events (AEs) that are new or worse than those at baseline (before treatment) after initiation of the study drugs. Only TEAEs will be summarized, and all AEs will be listed.

Drug-related TEAE (ADR) is defined as TEAE having the causal relationship of "*treatment-related*" with study drugs. In this trial, the definition of "*treatment-related*" is as follows: It refers to the relationship with the study drugs: related, possibly related, and unassessable. If the relationship between the AE and the study drugs is missing, the AE will be considered as an ADR.

AEs will be ranked from high to low according to the proportion of SOC/Cluster occurrence (total populations receiving the treatment), from high to low according to the proportion of PT under SOC (total populations receiving the treatment), and in alphabetical order if the incidences of at least 2 PTs are equal. If there is no AE under an SOC/Cluster or PT, the analysis will not be performed. Refer to Appendices 4 and 5 for the definition of Cluster classification.

In AE summary table, AEs after study drug treatment are analyzed according to the population, and the frequency and proportion are used for statistical description. AEs will be summarized using descriptive statistics according to Hengrui's Statistical Analysis Reporting Standards, including but not limited to the following contents:

- Any TEAE
- Treatment-related TEAE
- Any TESAE
- Treatment-related TESAE
- Grade  $\geq 3$  TEAE according to CTCAE grading
- Grade  $\geq 3$  treatment-related TEAE according to CTCAE grading
- Any TEAE  $\geq 5\%$
- Treatment-related TEAE  $\geq 5\%$
- TEAE leading to SHR-1210 treatment discontinuation and interruption

- TEAE leading to apatinib treatment discontinuation, treatment interruption, and dose reduction
- TEAE leading to death
- TEAE of special interest (AESI, the preferred term for AE provided by medical monitor, see Appendix 2 for details; other Grade  $\geq 3$  immune-related adverse events (irAEs): meeting irAE definition requirements and Grade  $\geq 3$  according to CTCAE v4.03)

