- Immune-related TEAE (irAE, including two categories: 1) AE that the investigators determine to be related to SHR-1210 (including definitely related, possibly related, and indeterminable) and corrected with glucocorticoid drugs (except reactive capillary endothelial proliferation); 2) other irAEs that the investigators determine to be related to SHR-1210 without the use of glucocorticoids, with the preferred term for AE provided by medical monitor, see Appendix 3 for details)
- The selected TEAE (the preferred term for AE provided by medical monitor, see Appendix 4 for details)
- The selected TEAE that the investigators determine to be related to SHR-1210 (the preferred term for AE provided by medical monitor, see Appendix 5 for details) and glucocorticoid utilization rate
- No subject with TEAE leading to interruption, dose reduction, and termination of two drugs
- TEAE leading to treatment interruption (apatinib or SHR-1210)
- TEAE leading to treatment termination of two drugs

The incidence of AE is calculated based on the number of subjects having an AE, instead of the number of AE episodes.

AESIs include:

- Grade  $\geq 3$  infusion reaction
- Grade  $\geq 2$  diarrhea/colitis, uveitis, and interstitial pneumonia
- Other Grade  $\geq 3$  irAEs
- Liver enzyme abnormal event: ALT, AST, and total bilirubin (TBIL) are abnormal against baseline
- Grade 4 amylase or lipase increased
- Reactive capillary endothelial proliferation

Among them, the specific definition of liver enzyme abnormal events is as follows:

Baseline Period	Normal (AST/ALT and TBIL)	Abnormal (AST/ALT/TBIL)
Treatment Period	ALT or AST $\geq 3 \times \text{ULN}$ with TBIL $\geq 2 \times \text{ULN}$ and ALP $\leq 2 \times \text{ULN}$ and without hemolysis	AST or ALT $\geq 2 \times \text{baseline level}$ , and $\geq 3 \times \text{ULN}$ or AST or ALT $\geq 8 \times \text{ULN}$ with TBIL increase $\geq 1 \times \text{ULN}$ or TBIL $\geq 3 \times \text{ULN}$

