The selected AEs are analyzed separately. For each selected AE, the time to first event (weeks) is summarized in the form of continuous variables, that is, mean, standard deviation, median, maximum, minimum, and quartile (Q1 and Q3) are used for the summary. The greatest grade and the measures taken to study drugs are summarized in the form of categorical variables. The events are also summarized according to factors such as TEAE severity and TEAE occurrence cycle, respectively. The number and percentage of subjects who experience each selected AE and have been resolved are summarized.

The calculation method for the cycle length of TEAE which occurs is:

(Starting date of TEAE - date of first administration + 1) / 28 + 1, and the integer part will be retained;

Time to first event (weeks) = (date of first event occurrence - date of first administration + 1) / 7.

All AEs will be listed. Treatment-related AEs, AEs that result in treatment termination, AEs that result in treatment delay or dose reduction, and death will be listed separately.

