### Preferred Term List of Selected Treatment-Related Adverse Drug Reaction

Cluster Term	MedDRA Preferred Term
Reactive capillary endothelial proliferation	Reactive capillary endothelial proliferation
Selected endocrine-related adverse events (drug related)	Adrenal insufficiency
Selected endocrine-related adverse events (drug related)	Cortisol increased
Selected endocrine-related adverse events (drug related)	Diabetes mellitus
Selected endocrine-related adverse events (drug related)	Blood glucose increased
Selected endocrine-related adverse events (drug related)	Hyperglycemia
Selected endocrine-related adverse events (drug related)	Ketoacidosis
Selected endocrine-related adverse events (drug related)	Lymphocytic hypophysitis
Selected endocrine-related adverse events (drug related)	Hypophysitis
Selected endocrine-related adverse events (drug related)	Thyroiditis
Selected endocrine-related adverse events (drug related)	Thyroid function test abnormal
Selected endocrine-related adverse events (drug related)	Lymphocytic hypophysitis
Selected endocrine-related adverse events (drug related)	Immune-mediated endocrinopathy
Selected endocrine-related adverse events (drug related)	Primary hypothyroidism
Selected endocrine-related adverse events (drug related)	Hypothyroidism
Selected endocrine-related adverse events (drug related)	Hyperthyroidism
Selected endocrine-related adverse events (drug related)	Blood thyroid stimulating hormone increased
Selected endocrine-related adverse events (drug related)	Thyroxine free decreased

Cluster Term	MedDRA Preferred Term
Selected endocrine-related adverse events (drug related)	Blood thyroid stimulating hormone decreased
Selected endocrine-related adverse events (drug related)	Thyroxine free increased
Selected liver-related adverse events (drug related)	Aspartate aminotransferase increased
Selected liver-related adverse events (drug related)	Alanine aminotransferase increased
Selected liver-related adverse events (drug related)	Hepatic function abnormal
Selected liver-related adverse events (drug related)	Bilirubin conjugated increased
Selected liver-related adverse events (drug related)	Hyperbilirubinemia
Selected liver-related adverse events (drug related)	Blood bilirubin unconjugated increased
Selected liver-related adverse events (drug related)	Liver injury
Selected liver-related adverse events (drug related)	Blood bilirubin abnormal
Selected liver-related adverse events (drug related)	Bilirubin total increased

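### SAP Appendix 4 has no cluster for hypertension, proteinuria, hand-foot syndrome, thrombocytopenia, bleeding, thromboembolism or perforation, so these apatinib harms get no pooled rate, onset or resolution summary

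*SAP*

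**What the plan says.** SAP 5.5.2 defines one group of events by reference to a list: "The selected TEAE (the preferred term for AE provided by medical monitor, see Appendix 4 for details". It sends the reader to the appendices for pooling as well: "Refer to Appendices 4 and 5 for the definition of Cluster classification". The group then gets its own analysis: "The selected AEs are analyzed separately". That analysis covers onset ("For each selected AE, the time to first event (weeks) is summarized in the form of continuous variables"), severity and action ("The greatest grade and the measures taken to study drugs are summarized in the form of categorical variables"), occurrence by cycle, and the number and percentage of affected subjects whose event resolved.

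Appendix 4 is headed "Preferred Term List of Selected Treatment-Related Adverse Drug Reaction". Appendix 5 is a separate, shorter list for events related to SHR-1210.

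The protocol describes apatinib's own toxicity in several places. Of the ongoing phase III trial in hepatocellular carcinoma, section 1.1 says: "Adverse events that have been observed include proteinuria, elevated blood pressure, thrombocytopenia, hand-and-foot syndrome, and elevated total bilirubin". Section 5.3 gives its examples as "If apatinib-related AE occurs during the study, such as hypertension, proteinuria, or hand-and-foot syndrome". Section 9.3, on apatinib-related reactions, has items on hand-foot syndrome, hypertension, haemorrhage, proteinuria and thrombosis, and covers gastrointestinal perforation under abdominal pain.

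**The concern.** The regimen combines two drugs with different toxicity profiles, and Appendix 4 is headed as covering either of them. Since Appendix 5 already serves SHR-1210, Appendix 4 is the one list in which apatinib's characteristic harms could be clustered. Its clusters largely follow the anti-PD-1 pattern instead.

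Safety is a secondary objective, and protocol 5.3 lets a subject continue on one drug after toxicity to the other. When apatinib's characteristic harms begin, and how often they resolve, are therefore useful parts of the combination's safety description. A harm recorded under several preferred terms also needs a count of subjects with any of them, because rates for the separate terms cannot simply be added.

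**Working it through.** The plan states no figure on this point, so the check is an audit of terms, followed by one illustration.

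**1. Content of Appendix 4.** Rows by cluster: reactive capillary endothelial proliferation 1, endocrine 19, liver 15, skin 10, digestive tract 5, infusion reaction 2, lung 3, myocarditis 1, kidney 3.

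1 + 19 + 15 + 10 + 5 + 2 + 3 + 1 + 3 = 59 rows, or 58 distinct terms because lymphocytic hypophysitis appears twice.

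**2. The protocol's apatinib harms against those rows.**

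| Harm | Where the protocol names it | Rows in Appendix 4 |
|---|---|---|
| Hypertension | 1.1, 5.3, Table 1, 9.3 | 0 |
| Proteinuria | 1.1, 5.3, Table 1, 9.3 | 0 |
| Hand-foot syndrome | 1.1, 5.3, Table 1, 9.3 | 0 |
| Thrombocytopenia | 1.1 (within haematological toxicity in Table 1) | 0 |
| Haemorrhage | 5.3, 9.3 | 0 |
| Arterial or venous thrombosis | 5.3, 9.3 | 0 |
| Gastrointestinal perforation | 5.3, 9.3 | 0 |

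The nearest clusters do not help. The kidney cluster holds creatinine increased, glomerular filtration rate decreased and renal impairment, with no urine-protein term. The skin cluster has no hand-foot term. Appendices 2, 3 and 5 contain none of the seven harms either.

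**3. What the other planned outputs supply.**

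- The adverse event tables in 5.5.2 (all events, treatment-related, serious, Grade 3 or above, fatal) give incidence by system organ class and preferred term, counting a subject once within each.
- A further table covers events leading to apatinib discontinuation, interruption or dose reduction, so action taken on apatinib is summarised.
- Laboratory shift tables (5.5.3) cover haematology, urinalysis, stool and coagulation. They use three categories (normal, abnormal without clinical significance, abnormal with clinical significance), not CTCAE grades. Continuous tests are also summarised by visit.
- Vital signs, including blood pressure, get descriptive statistics (5.5.4).

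Against the selected-event analysis, three things are missing for the seven harms: a rate pooled over related terms with each subject counted once, time to first event, and resolution.

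**4. Why pooling matters most for bleeding.** Section 9.3 of the protocol itself names gastrointestinal, pulmonary and cerebral bleeding. Coding by organ system puts such terms in different classes, so neither a preferred-term row nor a class row brings them together. The documents give no bleeding rate, so the rates, the number of terms and independence below are all assumptions. For k terms each with rate p, the pooled rate under independence is 1 − (1 − p)^k:

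- k = 5, p = 3%: 1 − 0.97^5 = 1 − 0.859 = 14.1%
- k = 5, p = 4%: 1 − 0.96^5 = 1 − 0.815 = 18.5%

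Without independence, the pooled rate can lie anywhere from p (the same subjects have every term) to k × p (no subject has two): 3% to 15% in the first case, 4% to 20% in the second. In both cases every single term misses the 5% table.

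**The case against.** The strongest reply is that little is lost. A reader might infer from Appendix 4 that these harms go unreported, or appear only as single preferred-term rows. The documents do not support that: the outputs in step 3 of the working include a table aimed at apatinib specifically, and laboratory and blood pressure data that do not depend on adverse event coding.

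Nor is the selected list confined to immune-mediated events, or silent on everything that leads to apatinib being held. Protocol Table 1 suspends apatinib for transaminase and bilirubin elevation, and the 15-term liver cluster covers both. Diarrhoea, which section 1.1 lists among apatinib's main reactions, is in the digestive cluster.

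No protocol commitment is breached. The safety endpoints ask for incidence and severity, laboratory abnormalities, and events causing interruption or discontinuation. Protocol 11.5.4 asks for categorised summaries of immune-related events only, and the events of special interest in protocol 8.4 include none of the seven harms. Protocol 7.2.2 also recommends clinical over laboratory terms, which should reduce splitting between, for example, thrombocytopenia and a low platelet count.

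Finally, the list of summaries in 5.5.2 is expressly non-exhaustive and follows sponsor reporting standards that are not in the documents.

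All of this stands, and it narrows the point. It does not supply a pooled rate, onset or resolution for the omitted harms. A non-exhaustive list permits additions but does not prespecify their terms, and terms chosen after the data are seen carry less weight. The recommendation in 7.2.2 does nothing for bleeding at different sites.

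**Conclusion.** The gap is real and limited. For seven kinds of harm that the protocol attributes to apatinib or lists as reasons to stop it, the planned outputs give no once-per-subject pooled rate, no time to first event and no resolution summary. The selected-event analysis does give these for liver, endocrine, skin and the other listed clusters.

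The loss is uneven. For bleeding it is chiefly the pooled rate. For a near-single-term event such as hand-foot syndrome, a cluster would hardly change the incidence, and the loss is mainly onset and resolution.

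The absence of terms is a direct count (0 of 59 rows) and rests on no assumption. The 14% figure is an illustration only. A reader might infer from it that combined bleeding will be well above 5%, but nothing in the documents says so. Low-frequency terms would also leave only the 5% tables; they would remain in the table of all events.

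This is a cheap improvement to safety reporting. It does not affect the primary endpoint or show an error in the protocol's safety endpoints.

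**What to change.** Add clusters to Appendix 4, and to the selected-event tables of SAP 5.5.2, for hypertension, proteinuria, hand-foot syndrome, thrombocytopenia (including platelet count decreased), haemorrhage, arterial and venous thromboembolism, and gastrointestinal perforation. Define each by a MedDRA v24.0 preferred-term list or a standardised MedDRA query, and state that a subject counts once per cluster. The existing summaries of onset, greatest grade, action taken and resolution then apply to them unchanged.

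The cost is a term review by the medical monitor and a few more tables. SAP version 2.0 already revised Appendices 2 to 5 for the dictionary upgrade, so the route exists. No new data are needed, and no dosing or clinical rule changes.

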8.1.3. Determination of the relationship between AEs and the investigational drug

The potential relationship between the AE and the investigational drug was assessed with 5 grades of causality: definitely related, possibly related, unlikely related, not related and indeterminable. "Definitely related", "possibly related", and "not assessable" events are included as adverse drug reactions. The incidence of AEs is calculated with the sum of these three categories as the numerator and the number of subjects for safety evaluation as the denominator.

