##### **5.1.1.2. Safety analysis set (SS)**

All enrolled subjects who have received the study drugs at least once are included in the safety analysis set. This dataset is used for safety analysis.

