## **5.5. Safety Analysis**

All safety analyses are conducted based on safety analysis set.

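### The by-cycle summary of selected adverse events gives no number at risk, so its figures fall with attrition and cannot be read as the time course of risk

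*SAP*

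**What the plan says.** SAP 5.5.2 analyses the selected adverse events separately. It asks for time to first event as a continuous summary, the worst grade, the action taken and the proportion resolved. It then adds: "The events are also summarized according to factors such as TEAE severity and TEAE occurrence cycle, respectively". The cycle comes from a calendar formula, "Starting date of TEAE - date of first administration + 1) / 28 + 1", with the integer part kept. It therefore runs in 28-day blocks from first dose, whether or not the subject is still treated.

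Four other rules bear on that table:

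- **Population.** SAP 5.5: "All safety analyses are conducted based on safety analysis set". SAP 5.1.1.2 defines the set: "All enrolled subjects who have received the study drugs at least once are included in the safety analysis set".
- **Form of summary.** For the adverse event summary table, SAP 5.5.2 says: "AEs after study drug treatment are analyzed according to the population, and the frequency and proportion are used for statistical description".
- **Counting.** SAP 5.5.2: "The incidence of AE is calculated based on the number of subjects having an AE, instead of the number of AE episodes". Within a system organ class or preferred term, "multiple cases of the same events occurred in one subject will be counted only once".
- **Denominator.** Protocol 8.1.3, on adverse drug reactions, takes "the number of subjects for safety evaluation as the denominator".

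Neither document specifies a per-cycle number at risk, an exposure-adjusted rate or a cumulative-incidence estimate for adverse events.

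**The concern.** A table of events by cycle invites the reader to see when the risk is highest. SHR-1210 may be given for up to 2 years, and the protocol's schedule runs to cycle 26. Subjects leave earlier for progression, toxicity, withdrawal and other reasons (Protocol 4.3.1). Events in late cycles can come only from those still observed, while the population named for the analysis stays at everyone dosed. The once-per-subject rule adds a second loss, because a subject already counted for an event cannot contribute it again.

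Both effects push late figures down. Immune, hepatic and skin toxicity would look concentrated in early cycles even with a flat risk, and a reader could take late treatment to be safer than it is.

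**Working it through.** The documents give no figure for this table, so there is none to reproduce. The check asks what a constant risk would look like in it.

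**Inputs**
- Cycle length: 28 days. A month is 30.4375 days, as in the SAP.
- Time on treatment: assumed exponential with median m. The only figure in the documents is a median of more than 7 months in an earlier 14-patient study (Protocol 1.2.1). I take m = 7 and show 10 and 14, since 7 is a lower bound.
- Window w after the last dose: at least 30 days for adverse events, and 90 days after the last SHR-1210 dose for serious and immune-related events (Protocol 8.1.1). The model stops both drugs together and ignores death or new therapy within the window.
- True risk: assumed 5% per cycle, for illustration only. The attrition percentages do not depend on it.

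**Attrition.** The share still observed at the start of cycle c is 2^(−x), with x = [28(c−1) − w] / (30.4375 × m).

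For c = 13 and m = 7:
- w = 30: x = (336 − 30) / 213.06 = 1.436, share 0.37, understatement 63%.
- w = 90: x = (336 − 90) / 213.06 = 1.155, share 0.45, understatement 55%.

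Other cycles at m = 7:

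| Start of cycle | Understated, 30-day window | Understated, 90-day window |
|---|---|---|
| 7 | 36% | 22% |
| 13 | 63% | 55% |
| 19 | 79% | 74% |

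Cycle 13 with longer medians:
- m = 10: x = 306/304.375 = 1.005 and 246/304.375 = 0.808, so 50% and 43%.
- m = 14: x = 306/426.125 = 0.718 and 246/426.125 = 0.577, so 39% and 33%.

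**Depletion.** If an event counts once per subject over the whole study, the share still event-free at the start of cycle 12 is 0.95^11 = 0.57, and at cycle 13 it is 0.95^12 = 0.54. Dividing by subjects still observed, without removing those already counted, would therefore leave a spurious fall of about 43% by cycle 12.

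**Both together.** Take m = 7, the 30-day window, and events independent of staying on treatment. A true 5% then appears at cycle 13 as 5% × 0.37 × 0.54 = 1.0%. Averaged over the cycle, the cycle 12 figure is 0.22 of the cycle 1 figure; it is 0.29 at m = 10 and 0.35 at m = 14.

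**With an at-risk denominator.** Dividing first onsets by subjects both observed and event-free at the start of the cycle returns about 5% in every cycle under the same assumptions.

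**The case against.** The strongest reply is that the denominator is not stated. The by-cycle sentence gives no percentage. The frequency-and-proportion wording introduces the overall summary table, whereas the selected events are analysed separately. Naming the safety set as the population need not fix the denominator of every cell, and the sponsor's reporting standards, which the SAP cites, may set the layout. This stands: the fixed denominator is an inference. It does not remove the point, because bare counts by cycle would fall in the same way and no number at risk is provided for either form.

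A second reply is that leaving treatment is not leaving observation. This also stands. A reader might count only subjects still on treatment and infer an understatement of 66% at cycle 13. The documents do not support that, because collection continues for at least 30 days, and for 90 days for serious and immune-related events.

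Third, exposure (SAP 5.5.1), discontinuations with reasons (SAP 5.2.1) and time to first event are all reported. They make attrition visible, but none is tied to the by-cycle figures. Time to first event is summarised without censoring.

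Fourth, the share of all treated subjects with onset in a given cycle is a valid description of when events occurred, and the SAP never calls it a risk. This is fair, and it limits the point to how the table can be read.

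**Conclusion.** The point holds as a free improvement to a descriptive safety table. Without a per-cycle number at risk, the by-cycle figures decline under constant risk and cannot show the time course of toxicity. At an assumed 7-month median, attrition alone understates cycle 13 by about 63% (30-day window) or 55% (90-day window). At 14 months this becomes 39% or 33%. Depletion adds to this if the once-per-subject rule runs across cycles; if it is applied within each cycle, only attrition acts.

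The direction holds for any attrition. The size rests on the assumed duration and the exponential form.

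A reader might infer that the SAP prescribes a misleading percentage, or that late toxicity will go unreported. The documents support neither: the denominator is not printed, and all adverse events are listed. The trial is single-arm, no test or decision uses this table, and the ORR rule is untouched.

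**What to change.** In SAP 5.5.2, for each selected event and each cycle, print the number of safety-set subjects who at the start of the cycle are still under adverse event observation and still free of that event. Use it as the denominator for first-onset proportions. Define observation by the protocol's own windows: 30 days after the last dose for adverse events, and 90 days after the last SHR-1210 dose for serious and immune-related events. Apply the protocol's rule on new anti-tumor treatment. For the SHR-1210-related events in Appendix 5, base the window on SHR-1210 dosing dates, since either drug may continue alone.

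Alternatively, report all episodes per patient-cycle of observation. Either way, state whether the once-per-subject rule applies within a cycle or across the study.

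Use the same cycle boundaries for events and for the number at risk. As written, the cycle formula puts study day 28 in cycle 2 (28/28 + 1 = 2), one day early.

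The cost is a few lines of SAP text and one derived variable from dosing, event, death and subsequent-therapy dates that are already collected.
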